#### **9.4.5.4. Vital Signs, ECG, Physical Examination and Other Safety Data**

Vital signs, ECG, physical examination, and C-SSRS data will be summarized for the safety analysis set at screening, baseline, and each time point during the treatment period using appropriate descriptive statistics. Changes from baseline to each post-baseline visit will also be summarized for vital signs and ECG.

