**Part A:**

- The duration of study participation in Part A is approximately 26 weeks, which includes a 1- to 3-week screening period, 4-week baseline observation period, 14-week dose-optimization treatment period, 10-day taper period, and a safety follow-up period (4 weeks after end-of-taper visit).
- After the informed consent/assent form has been signed, participants will be screened to enter the study from Day -49 to Day -35 (Visit 1) and commence a 28-day baseline period beginning at Day -28 (Visit 2), before returning for a randomization visit and treatment initiation (Day 1 [Visit 3]).
- IMP administration during the 14-week treatment period will follow a flexible titration schedule to enable optimization of dosage.
- Visits 4 to 6 will be conducted as phone visits; Visit 7 will be completed in clinic, and Visit 8 will be completed in clinic or at home visit. Participants will then return to the study site for an end of treatment visit (Day 99 [Visit 9]). If a participant withdraws from the study prematurely (ie, before the end of treatment visit) an early withdrawal visit will be conducted, and a safety follow-up phone call will occur 4 weeks after their last dose of IMP. If a participant discontinues IMP prematurely, they should be encouraged to complete the end of treatment visit and the taper period and remain in the study. Participants not continuing to Part B of the study will return to the study site again at the end of the 10-day taper period (Day 110 [Visit 10]) and complete a phone safety visit at the end of the follow-up period (Day 138 [Visit 11]).
- Part B will be available to participants who complete Part A of the study and continue to meet all eligibility criteria and to participants for whom the investigator feels continued treatment in Part B represents a favorable risk-benefit assessment. Rollover into Part B should occur on the same day as Part A Day 99 (Visit 9).
- Unscheduled phone visits can occur at any time throughout Part A, as needed.

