### **Brief Summary:**

The purpose of this study is to assess the change from baseline in seizure frequency of twice daily (BID) doses of cannabidiol (CBD; GWP42003-P) compared with placebo in children and adolescents with EMAS. Study details include:

**Study Duration:** Approximately 80 weeks (Part A: 26 weeks and Part B: 54 weeks)

**Treatment Duration:** Up to approximately 66 weeks for Part A and Part B (Part A up to 16 weeks including the taper period and Part B up to 50 weeks, including the taper period)

**Visit Frequency:** Weekly or monthly (study site visits, home visits, or phone visits). GWP42003-P is not available through an expanded access program.

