### **Part B:**

All data collected during this part of the study will be summarized over time using appropriate descriptive statistics. Where baseline data are available from Part A, changes from baseline will also be presented as appropriate.

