#### **8.2.1.1. Columbia-Suicide Severity Rating Scale (4 Years of Age and Older)**

Suicidality will be assessed by using the C-SSRS or, in participants with profound cognitive impairment, by the investigator's clinical judgment following interview of the participant. Where the C-SSRS is not considered appropriate and clinical interview is used instead, the reason must be clearly documented by the investigator.

The definitions of behavioral suicidal events used in this scale are based on those used in the Columbia Suicide History Form. Questions are asked on suicidal behavior, suicidal ideation, and intensity of ideation. During screening (Part A Visit 1), questions will be in relation to lifetime experiences, and all subsequent questioning will be in relation to the last assessment (since last visit).

The C-SSRS is to be completed by the investigator or his/her qualified delegate at every visit as indicated in the SoA ([Section 1.3](#)); "qualified delegate" is defined as anyone who has completed the C-SSRS training within the past 2 years or has continually administered the C-SSRS assessments throughout this study since obtaining the training certificate. The survey should be completed by the same assessor, where possible, throughout the study.

The C-SSRS will be used for participants aged 4 to 18 years (inclusive). If a participant is unable to provide adequate responses, the C-SSRS may be administered to the participant's caregiver to obtain responses on behalf of the participant.

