### **8.3.6. Suicidal Ideation and Behavior Risk Monitoring**

ASMs are associated with an increased risk of suicidal ideation or behavior.

Participants with EMAS may occasionally develop suicidal ideation or behavior.

Participants being treated with IMP should be monitored appropriately and observed closely for suicidal ideation and behavior or any other unusual changes in behavior, especially at the beginning and end of the course of IMP, or at the time of dose changes, either increases or decreases. All factors contributing to suicidal ideation or behavior should be evaluated and consideration should be given to discontinuation of the IMP.

Baseline assessment of suicidal ideation and behavior will be monitored during the study using C-SSRS or clinical interview if C-SSRS is not appropriate.

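### Section 9.4.5.4 ends the C-SSRS summary with the treatment period, so scheduled taper and follow-up ratings fall outside it, and no any-time participant count of suicidality is specified

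*Combined protocol and SAP*

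**What the plan says.** Section 9.4.5.4 sets the time points: "C-SSRS data will be summarized for the safety analysis set at screening, baseline, and each time point during the treatment period". The next sentence adds: "Changes from baseline to each post-baseline visit will also be summarized for vital signs and ECG". It does not name the C-SSRS.

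Collection runs longer than that summary. Section 8.2.1.1 states: "The C-SSRS is to be completed by the investigator or his/her qualified delegate at every visit as indicated in the SoA". Table 1 marks the C-SSRS at Part A Visits 1 to 11, and Table 2 marks it at Part B Visits 1 to 12. The last two visits in each part are end of taper and safety follow-up. After the lifetime questions at screening, "all subsequent questioning will be in relation to the last assessment (since last visit".

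The synopsis lists the Part A periods separately: "14-week dose-optimization treatment period, 10-day taper period, and a safety follow-up period (4 weeks after end-of-taper visit". Its Brief Summary gives treatment duration as "Part A up to 16 weeks including the taper period".

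Two other places bear on scope. For Part B, the statistical part of the synopsis says: "All data collected during this part of the study will be summarized over time using appropriate descriptive statistics". Section 8.3.6 asks for close observation for suicidality "especially at the beginning and end of the course of IMP, or at the time of dose changes".

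Change in C-SSRS ideation score and number of suicide attempts are secondary safety endpoints in Part A (Section 3.1) and primary endpoints in Part B (Section 3.2). The adverse-event endpoint in those lists is tied to the 14-week or 48-week treatment period. The C-SSRS endpoints carry no time limit.

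**The concern.** Taken literally, the analysis rule is narrower than the data collection. The ratings that cover dose reduction and the weeks after it are collected, but the section that says how the C-SSRS will be presented does not include them. Section 9.4.2 sends the reader to Section 9.4.5 for the presentation of the Part B primary safety endpoints, so the limit applies to a primary endpoint.

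The second gap concerns the unit of counting. A reader of the safety results will want to know how many children had any suicidal ideation or behaviour after starting the product. Section 2.3 lists suicidal behaviour and ideation among its serious side effects. The section describes summaries by time point only, and these cannot answer that question when each rating covers a different interval.

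Part A also offers the only placebo-controlled view of the taper and follow-up. Under Section 7.1, suicidal behaviour or C-SSRS item 4 or 5 ideation is a reason for removal from IMP, and participants who stop IMP early in Part A do not enter Part B. The Visit 10 and 11 ratings are therefore the ones due from such participants if they stay in the study.

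**Working it through.** The plan gives no figure for this point, so there is nothing to reproduce. The check counts scheduled ratings and days against the periods named in Section 9.4.5.4.

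**Inputs (Tables 1 and 2)**
- Part A: first dose at Visit 3 (Day 1); end of treatment at Visit 9 (Day 99); end of taper at Visit 10 (Day 110); follow-up at Visit 11 (Day 138).
- Part B: start at Visit 1 (Day 1); end of treatment at Visit 10 (Day 337); end of taper at Visit 11 (Day 348); follow-up at Visit 12 (Day 376).

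**Ratings outside the stated summary, with taper as a separate period**
- Part A: Visits 4 to 11 give 8 post-dose ratings. Visits 4 to 9 are in the treatment period, which leaves 8 − 6 = 2 outside (2/8 = 25%).
- Part B: Visits 2 to 12 give 11 ratings. Visits 2 to 10 are in the treatment period, which leaves 11 − 9 = 2 outside (2/11 = 18%).

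**Days not covered by any summarised rating**
- Part A: 138 − 99 = 39 days, or 39/137 = 28% of the span from Day 1. This applies to participants who do not roll over.
- Part B: 376 − 337 = 39 days, or 39/375 = 10% of the span. This applies to everyone who enters Part B and follows the schedule.

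The recall window is the time since the last visit, so no earlier rating reaches into these days.

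**If taper is counted as treatment**
- Part A: only Visit 11 is outside. 138 − 110 = 28 days; 1 of 8 ratings.
- Part B: only Visit 12 is outside. 376 − 348 = 28 days; 1 of 11 ratings.

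**What visit-level counts can say about participants**

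The number of distinct participants affected lies between the largest single-visit count and the sum of the visit counts. With one positive rating at each of the six Part A treatment visits (4 to 9), the lower bound is 1 (the same child each time) and the upper bound is 6 (six different children). The bound needs no assumed event rate.

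**Text comparison**

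Section 9.4.5.3, just before, summarises laboratory data at each visit. The change-from-baseline sentence in Section 9.4.5.4 reaches every post-baseline visit, but only for vital signs and ECG. Nothing in Section 9.4.5 extends the C-SSRS in the same way.

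**The case against.** The strongest reply is that Section 9.4 describes itself as a summary and leaves the detail to a SAP, no separate text of which is in the public document. Section 9.4.6 promises an analysis of all Part A data, and the synopsis promises a summary of all data in Part B. A reader might infer that the taper and follow-up ratings are discarded. The documents do not show that. What stands is that the one section stating the C-SSRS time points states a narrower scope than these general promises.

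A reader might also infer that taper-visit vital signs are lost. They are not: changes to each post-baseline visit are summarised for vital signs, and only the observed-value summary stops earlier. Nor is the C-SSRS summary confined to treatment visits, since screening and baseline are named.

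It would also be too strong to say that affected participants are never counted. Section 9.4.1 gives participant frequencies and proportions for categorical data. Adverse events are collected to the follow-up visit (Section 8.4.1), the treatment-emergent definition has no end date, and participants with at least one event are counted (Section 9.4.5.2). A suicidality event reported as an adverse event in taper or follow-up would therefore reach a participant-level table. A C-SSRS response not reported as an adverse event would not, and suicidality is not among the events of special interest in Section 10.4.3.

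Section 8.3.6 is an instruction for clinical monitoring, not an analysis rule, so it does not strictly contradict Section 9.4.5.4. It shows that the omitted period is one the protocol itself regards as important.

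Finally, the uncovered days are not all of the off-drug time. Participants who stop IMP early are encouraged to remain in the study, so some off-drug time falls within the treatment period.

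**Conclusion.** The point holds in a limited form. As written, the C-SSRS summary leaves out 2 of 8 post-dose ratings in Part A (participants not rolling over) and 2 of 11 in Part B, covering 39 scheduled days in each. If taper is read as part of treatment, it leaves out 1 of 8 and 1 of 11, covering 28 days in each. The follow-up visits are outside on either reading. For Part B this conflicts with the synopsis commitment on a primary safety endpoint. Separately, no any-time participant-level C-SSRS count is specified, and visit-level tables cannot supply one.

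The day counts assume visits on their nominal days and participants who follow the full schedule. It is tempting to put a percentage on how far visit tables understate the share ever affected. The documents give no per-visit rate and no basis for assuming independence between visits, so only the 1-to-6 bound is used here. The SAP may already close both gaps; the public text does not show it. This is worth correcting because the rule as stated points the wrong way and the data will already be in hand.

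**What to change.** In Section 9.4.5.4, for the C-SSRS, replace the restriction to the treatment period with *during the treatment, taper and safety follow-up periods*. This also brings the section into line with the synopsis for Part B.

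Add a table, by arm, of the number of participants with any suicidal ideation or behaviour after first dose, split into on-treatment and taper/follow-up. State the denominator, since Section 8.2.1.1 limits the scale to ages 4 to 18. If the SAP already does this, a cross-reference is enough.

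Vital signs need no change on this account. The cost is a wording change and one or two extra tables; no new data or visits are needed.

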**Table 1: Schedule of Activities: Part A**

Study Period	Screening	Baseline Period	14-Week Dose-Optimization Treatment Period						EOT or E/W	Taper Period	Safety FU	Notes
Visit Number	1	2	3	4	5	6	7	8	9	10	11	
Week	-	-	0	1	2	3	4	8	14	16	20	
Day	-49 to -35	-28	1	8	15	22	29	57	99	110	138	
Visit Window (days)	-	-	+3	±3	±3	±3	±3	±7	±7	+3	±7	
Visit Type	Clinic	Phone	Clinic	Phone	Phone	Phone	Clinic	Clinic*	Clinic	Clinic	Phone	
Physical examination	X		X						X			Section 8.3.1 Includes measurement of height, length, and head circumference.
Serum pregnancy test	X											Section 8.3.5 May be performed more regularly if required by local regulations.
Urine pregnancy test			X						X			Section 8.3.5 Confirmed prior to first dose of IMP. May be performed more frequently if required by local regulations
Epilepsy gene panel			←————→									Section 8.7. Optional, only completed once.
Body weight			X				X	X	X			Section 6.5 and Section 8.3.1 .
Randomization			X									

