### **2.3. Benefit/Risk Assessment**

Participants in the current study may experience some improvement of symptoms (beyond that of an assessment of their medical status) from participating in the study. Refer to [Section 2.2](#) for details regarding antiseizure efficacy observed in previous epilepsy clinical studies with GWP42003-P, including patients with EMAS from the EAP. The risks of participation are primarily those associated with adverse reactions to the IMP, although there may also be some discomfort from collection of blood samples and other study procedures. More information about the known and expected benefits, risks, and reasonably anticipated AEs associated with GWP42003-P may be found in the current approved version of the IB (GWP42003-P IB).

GWP42003-P is purified CBD, approved in the US as Epidiolex®, indicated for the treatment of seizures associated with LGS, DS, and TSC in patients 1 year of age and older and approved in the EU, indicated for the adjunctive treatment of seizures associated with LGS and DS, in conjunction with clobazam, in patients 2 years of age and older and for adjunctive treatment of seizures associated with TSC in patient 2 years of age and older. The most commonly reported side effects include somnolence; decreased appetite; diarrhea; transaminase elevations; fatigue, malaise, and asthenia; rash; insomnia, sleep disorder, and poor-quality sleep; infections; pyrexia; and vomiting. Serious side effects include hepatocellular injury, somnolence and sedation, suicidal behavior and ideation, hypersensitivity reactions, and withdrawal of ASMs. Further information is included in the latest GWP42003-P (Epidiolex) United States Prescribing Information and/or Summary of Product Characteristics.

Overall, based on the extensive clinical safety and efficacy results of GWP42003-P demonstrated across 5 Phase 3 studies, 2 open-label studies, and the EAP in the treatment of pediatric epilepsy syndromes, it is believed that GWP42003-P has a favorable benefit-risk profile for the treatment of EMAS.

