#### Age and Sex

1. Participant must be male or female between 1 and 18 years of age, inclusive, at the time of initial informed consent/assent.
2. Participant must weigh at least 10 kg.

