#### **8.3.1. Physical Examinations**

A physical examination (including height, length, head circumference, and weight) will be performed at the time points specified in the SoA (see [Section 1.3](#)).

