#### **8.3.2. Vital Signs**

Vital signs will be measured in a supine position after 5 minutes rest in a quiet setting without distractions (eg, television, mobile phones) and will include body temperature, systolic and diastolic blood pressure, pulse rate, and respiratory rate. As part of screening procedures and at each clinic visit, blood pressure and pulse rate will also be taken after 2 minutes in a standing position (if it is possible for the participant to stand), following supine measurements. All measurements will be performed singly and repeated once if outside the relevant clinical reference range. Blood pressure must be recorded using the same arm throughout the study, where possible.

Additional vital signs measurements may be taken during the study, if clinically indicated.

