#### Overall Rationale for the Amendment:

The overall rationale for the changes implemented in Amendment 1.1 was to ensure alignment between study procedures and Italy Regulatory Agency guidance. Specific updates incorporated into Amendment 1.1 are listed below. Minor editorial changes are not presented.

Section # and Name	Description of Change	Brief Rationale
1.3 Schedule of Activities (SoA)	SoA: Part B: added physical examination for Week 14 (Month 3 visit) and Week 24 (Month 6 visit) study visits.	To have closer timelines for physical examination in Part B of the study.
	SoA: Part A and Part B: under column for "Notes" specified that height, length, and head circumference will be measured during physical examination.	To clarify that where physical examination appears now or was added, assessments for height, length, and head circumference will also occur.
	SoA: Part A and Part B: removed row for "Height/length."	For clarity since details regarding assessments for height, length, and head circumference during physical examination were included under column for "Notes."
	SoA: Part B Table Note: Text added specifying that "height, length, and head circumference will be collected at remote visits."	To clarify that these measurements will be collected during remote visits.
2.3 Benefit/Risk Assessment	Added a link to Section 2.2 (Study Rationale).	To outline the potential benefits of GWP42003-P.
	Added statement regarding favorable benefit-risk profile of GWP42003-P.	

Section # and Name	Description of Change	Brief Rationale
5.1 Inclusion Criteria	#2: An additional inclusion criterion specifying “minimum body weight required for eligibility” has been added.	To keep the blood volume within the maximum limits allowed during the study.
5.2 Exclusion Criteria	#25: Specified estimated glomerular filtration rate (Schwartz equation) < 60 mL/min.	To provide clarification per Health Authority request.
8.3.1 Physical Examinations	Specified that height, length, and head circumference will be collected during physical examinations.	
Table 6	Footnote “e” added to specify that estimated glomerular filtration rate will be calculated using the Schwartz equation.	

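### Section 9.4.5.4 limits change from baseline to vital signs and ECG, and no available text standardises growth for age and sex, so modest effects on weight or growth could be missed, most of all in uncontrolled Part B

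*Combined protocol and SAP*

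**What the plan says.** - **Population.** Section 5.1: "Participant must be male or female between 1 and 18 years of age, inclusive, at the time of initial informed consent/assent".
- **Where growth is measured.** Section 8.3.1: "A physical examination (including height, length, head circumference, and weight) will be performed at the time points specified in the SoA". In the Part A schedule (Table 1) the physical examination is marked at Visits 1, 3 and 9, with the note "Includes measurement of height, length, and head circumference". Body weight has its own row, marked at Visits 3, 7, 8 and 9. For Part B, the Amendment 1.1 history in Section 10.8 records "added physical examination for Week 14 (Month 3 visit) and Week 24 (Month 6 visit) study visits", and Table 2 marks body weight at most clinic visits.
- **What counts as a vital sign.** Section 8.3.2 says that vital signs "will include body temperature, systolic and diastolic blood pressure, pulse rate, and respiratory rate". Weight and height are not among them.
- **Analysis.** Section 9.4.5.4: "Vital signs, ECG, physical examination, and C-SSRS data will be summarized for the safety analysis set at screening, baseline, and each time point" in the treatment period, using descriptive statistics judged appropriate. The next sentence is "Changes from baseline to each post-baseline visit will also be summarized for vital signs and ECG".
- **Part B.** The Part B statistical paragraph of the synopsis covers all data from that part. It provides for changes from baseline, as appropriate, where a Part A baseline exists. Section 9.4.1 makes the Part A baseline the Part B baseline.
- **Known effects.** Section 2.3: "The most commonly reported side effects include somnolence; decreased appetite; diarrhea". Vomiting is also listed.

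**The concern.** Read together, Sections 8.3.1, 8.3.2 and 9.4.5.4 leave the growth measures out of the change-from-baseline sentence. A programmer who follows 9.4.5.4 would produce weight and height by visit and stop there.

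That summary is weak for children aged 1 to 18. In Part A, the spread between a toddler and an adolescent is far larger than any plausible 14-week drug effect. In Part B every participant receives active drug for 48 weeks. Average weight and height should rise with normal growth, so slowed growth can still appear as an increase. Change from baseline alone does not solve this; a reference for age and sex is needed.

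Long-term safety is the primary objective of Part B, and the product has known effects on appetite and the gut. The data needed to look for slowed growth or weight gain are already collected. What is at stake is whether the tables can show it.

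**Working it through.** The documents give no figure on growth, so there is none to reproduce. The check has a textual part and an illustrative part.

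**1. Which measures get change from baseline**

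| Domain | By-visit summary | Change from baseline stated |
|---|---|---|
| Laboratory data, including IGF-1 (9.4.5.3, Table 6) | Yes | Yes, with percent change and shift tables |
| Vital signs and ECG (9.4.5.4) | Yes | Yes |
| Physical examination, including growth (9.4.5.4), Part A | Yes | No |
| Physical examination, including growth, Part B | Yes | Not in 9.4.5.4; the synopsis allows it as appropriate |

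No available text mentions z-scores, percentiles, growth velocity or any other standardisation for age and sex.

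**2. Precision in Part A**

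From the documents: 1:1 allocation and at most 60 per arm. Assumed: SD of weight across ages 1 to 18 of 10–20 kg, and SD of the 14-week change in weight of 0.8–1.5 kg.

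95% half-width for the arm difference = 1.96 × SD × √(2/n). With n = 60 per arm, 1.96 × √(2/60) = 0.358.

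| Quantity | SD (kg) | Half-width (kg) |
|---|---|---|
| By-visit weight | 10 / 15 / 20 | 3.58 / 5.37 / 7.16 |
| Change in weight | 0.8 / 1.0 / 1.5 | 0.29 / 0.36 / 0.54 |

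The gain in precision is the ratio of the SDs, whatever the sample size. It runs from 10/1.5 = 6.7 to 20/0.8 = 25, so about 7- to 25-fold.

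If accrual stopped at the first interim look (60 randomised, about 30 per arm), the multiplier becomes 1.96 × √(2/30) = 0.506. The half-widths are then 5.1–10.1 kg on by-visit weight and 0.40–0.76 kg on change.

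**3. The same contrast as power, for scale only**

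Take an assumed 1 kg shortfall on active at 60 per arm, with power = Φ(1/(SD × √(2/60)) − 1.96).

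- By-visit weight: SD 10 kg gives Φ(0.548 − 1.96) = 7.9%; SD 20 kg gives Φ(0.274 − 1.96) = 4.6%.
- Change, with a wider assumed SD of 1–2 kg: SD 1 kg gives Φ(5.48 − 1.96), over 99.9%; SD 2 kg gives Φ(2.74 − 1.96) = 78%.

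The plan makes no such test. The figures only show how much information each summary carries.

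**4. Part B**

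Assume a normal gain of 2–4 kg over 48 weeks. With a 1 kg shortfall the observed change is 2 − 1 = 1 kg to 4 − 1 = 3 kg, which is still a gain. Neither by-visit weight nor unstandardised change would mark it as a shortfall. A z-score would fall, because it compares each child with the growth expected at that age and sex.

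**The case against.** A reader might infer that the plan has no change from baseline for growth at all, that values must be tabulated raw, and that a drug effect on growth would go unseen. The documents do not support that reading.

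- **Part B.** The synopsis allows change from baseline for Part B data, and growth has a Part A baseline. The gap in change from baseline is exact for 9.4.5.4 and for Part A, not for the whole document. The synopsis sentence does not supply standardisation, however, and 9.4.5.4 does not repeat it.
- **Wording.** Section 9.4.5.4 says only that the statistics will be appropriate. Unstandardised values are the natural reading, not an explicit statement.
- **Deferred detail.** Section 9.4 calls itself a summary and leaves detail to the SAP and Adaptive Design Report. No separate SAP is in the available text and some passages are blacked out, so silence elsewhere cannot be shown. This stands. Even so, the sentence that is stated names two domains for change and omits growth.
- **Other cover.** Part A has a placebo arm, and with complete data a reader could subtract by-visit means. That gives a mean change without its spread and shows no individual falls. Worsening judged clinically significant is an adverse event (Section 10.4.1), but someone must recognise it. IGF-1 is summarised as change but is not a growth measurement. Marked effects could well be seen.
- **Endpoints.** Growth is not a listed Part B endpoint, so the link to the primary objective is through long-term safety in general.
- **Size.** Every SD is assumed, safety analysis is descriptive, and the precision figures compare by-visit weight with change. They do not measure the gain from z-scores, for which step 4 gives only a reasoned illustration.

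**Conclusion.** The point holds in limited form. In Part A, Section 9.4.5.4 gives growth measures by-visit summaries without change from baseline. In Part B, the synopsis permits change, but no available text standardises for age and sex. Modest effects on weight or growth could be missed, particularly over 48 uncontrolled weeks.

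Under the assumed SDs, change from baseline is about 7- to 25-fold more precise than by-visit weight for the Part A arm difference. The exact ratio depends on those SDs, but the direction holds across the whole range. The Part B argument rests on an assumed normal gain of 2–4 kg.

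A fall in z-score in Part B could not be called drug-related. There is no control arm, and participants on a ketogenic diet are eligible. The primary efficacy analysis is unaffected. The change is worth making because it serves the safety objective with data already collected.

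**What to change.** In Section 9.4.5.4, and in the SAP, add descriptive summaries of change from the Part A baseline in weight, height/length and head circumference:

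- as observed, and as age- and sex-specific z-scores against a named growth reference, used for each measure only within the ages that the reference covers;
- by arm in Part A and over time in Part B;
- with counts of participants whose z-score falls by a prespecified amount (0.5 or 1 SD, for example).

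Align 9.4.5.4 with the Part B paragraph of the synopsis so that both say the same about change from baseline. State that Part B falls are reported descriptively and not attributed to the drug.

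The cost is extra programming, with no added visit or measurement. Home-nurse visits do not list weight among their tasks (notes to Tables 1 and 2), so some interim weights may be absent. The tables should use weights actually measured and show the number contributing at each visit. The end-of-treatment visits in both parts are scheduled in clinic.
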